6.2.3 Dose reduction steps for NIR178

Dose reduction steps for NIR178 are detailed in [Table 6-5](#) based on the starting dose of 240 mg. Of the first 10 patients enrolled at the NIR178 240mg dose across all tumor types, if more than 33% of the patients experience grade 3 or higher suspected to be related adverse events, subsequent patients will start treatment at NIR178 160mg twice daily. Patients enrolled at the NIR178 240mg dose will be monitored on an ongoing basis for emerging toxicities.

Table 6-5 Dose reduction steps for NIR178

The following table should be used as a dose reduction guide for patients receiving NIR178 capsule formulation (hard gelatin capsules):

[figure not shown]
Dose reduction*				
	Starting dose level	Dose level – 1	Dose level -2	Dose level – 3
NIR178	240 mg	160 mg	120 mg	80mg**
*Dose reduction should be based on the worst toxicity demonstrated at the last dose.				
**Dose reduction below 80 mg is not allowed. Altering from initial dosing schedule for NIR178 is not allowed.				

The following table should be used as a dose reduction guide for patients receiving NIR178 160 mg or 240 mg BID film coated tablet (FCT) formulation:

Dose reduction*			
	Starting dose level	Dose level – 1	Dose level – 2
NIR178	240 mg	160 mg***	80 mg**
*Dose reduction should be based on the worst toxicity demonstrated at the last dose.			
**Dose reduction below 80 mg is not allowed. Altering from initial dosing schedule for NIR178 is not allowed.			
***The first 10 patients enrolled in Part 3 of the study will be treated with the NIR178 160mg dose of the FCT formulation. A safety and PK analysis will be conducted to decide whether to increase the NIR178 dose to 240mg BID or complete Part 3 with NIR178 160mg BID.			

6.3 Concomitant medications

In general, concomitant medications and therapies deemed necessary for the supportive care (e.g. such as anti-emetics, anti-diarrhea) and safety of the patient are allowed. The patient must be told to notify the investigational site about any new medications, herbal remedies and dietary supplements he/she takes after the start of the study treatment. All medications (other than study treatment) and significant non-drug therapies (including physical therapy, herbal/natural medications and blood transfusions) administered during the study must be listed on the Prior and Concomitant Medications or the Surgical and Medical Procedures CRF.

Prior antineoplastic therapies including medications, radiotherapy, and surgery are to be recorded on the separate Prior Antineoplastic Therapy eCRF during screening.

6.3.1 Permitted concomitant therapy

The patient must be told to notify the investigational site about any new medications he/she takes after the start of the study drug. All medications (other than study drug) and significant non-drug therapies (including physical therapy, herbal/natural medications and blood transfusions) administered during the study must be listed on the Concomitant Medications or the Procedures and Significant Non-Drug Therapies CRF.

6.3.2 Permitted concomitant therapy requiring caution and/or action

NIR178 was demonstrated to be an inhibitor of CYP1A2 *in vitro*. Caffeine is a sensitive substrate of CYP1A2. Caution should be exercised if caffeine or caffeine containing food, beverages, or medications are consumed. Additionally, NIR178 was demonstrated to be a substrate of CYP1A2, therefore moderate and weak inhibitors of CYP1A2 should be used with caution.

NIR178 inhibited BCRP-mediated transport *in vitro*. Even though the risk of systemic inhibition of BCRP (e.g., liver, brain, and kidney) is predicted to be minimal to none, the potential risk of intestinal BCRP inhibition by NIR178 administered at clinically relevant doses cannot be ruled out. Therefore, concomitant administration of NIR178 with medications that are substrates of BCRP is permitted however caution should be exercised by the investigators ([Table 14-2](#)).

Anticoagulation is permitted if the patients are already at stable doses for >2 weeks at time of first dose and INR should be monitored as clinically indicated per investigator's discretion. However, ongoing anticoagulant therapy should be temporarily discontinued to allow tumor biopsy according to institutional guidelines.

Anti-hypertensives are allowed as concomitant medications; however, because transient hypotension has occurred during infusions of monoclonal antibodies, consideration should be given to withholding anti-hypertensive medications for 12 hours prior to infusion with PDR001.

[figure not shown]
Please see [Appendix 1](#) for further details.

6.3.3 Prohibited concomitant therapy

During the course of the study, patients must not receive other additional investigational drugs, agents, devices, chemotherapy, or any other therapies that may be active against cancer. However, limited-field palliative radiotherapy to non-target lesion(s) may be allowed as concomitant therapy following a documented discussion with Novartis. Such local therapies administered during the study treatment must be listed on the Concomitant radiotherapy/surgery case report form (CRF) page. Additionally, other therapeutic monoclonal antibodies and immunosuppressive medications are prohibited.

GnRH therapy to maintain effective testosterone suppression levels is allowed for mCRPC patients.

The use of systemic steroid therapy and other immunosuppressive drugs is not allowed except for the treatment of an infusion reaction, irAEs, for prophylaxis against imaging contrast dye

allergy or replacement-dose steroids in the setting of adrenal insufficiency (providing this is ≤ 10 mg/day prednisone or equivalent), or transient exacerbations of other underlying diseases such as chronic obstructive pulmonary disease (COPD) requiring treatment for < 3 weeks. Systemic corticosteroids required for the control of infusion reactions or irAEs must be tapered and be at non-immunosuppressive doses (≤ 10 mg/day of prednisone or equivalent) before the next study drug administration. If more than 10 mg/day prednisone is used, study treatment should be suspended. Topical, inhaled, nasal and ophthalmic steroids are allowed.

The use of live vaccines is not allowed through the entire duration of the study. Inactivated vaccines are allowed.

As previously discussed, NIR178 was found to be an inhibitor and substrate of CYP1A2 in vitro. Therefore, strong inhibitors and moderate inducers of CYP1A2 as well as sensitive (except caffeine) and narrow therapeutic index substrates of CYP1A2 are prohibited.

Additionally, medications known to cause Torsades de pointes and prolong the QT interval are prohibited.

Please see [Appendix 1](#) for further details.

6.4 Patient numbering, treatment assignment or randomization

6.4.1 Patient numbering

Each patient is identified in the study by a Subject Number (Subject No.), that is assigned when the patient is first enrolled for screening and is retained as the primary identifier for the patient throughout his/her entire participation in the trial. The Subject No. consists of the Center Number (Center No.) (as assigned by Novartis to the investigative site) with a sequential patient number suffixed to it, so that each subject is numbered uniquely across the entire database. Upon signing the informed consent form, the patient is assigned to the next sequential Subject No. available to the investigator through the Oracle Clinical RDC interface.

The investigator or designated staff will contact the IRT and provide the requested identifying information for the patient to register them into the IRT. Once assigned, the Subject No. must not be reused for any other subject and the Subject No. for that individual must not be changed, even if the patient is re-screened. If the patient fails to be randomized or start treatment for any reason, the reason will be entered into the Screening Disposition page.

[figure not shown]
IRT must be notified within 2 days that the patient was not randomized or did not start treatment.

For Japanese safety run-in part: Patients will be assigned by Novartis manually, outside IRT system.

6.4.2 Treatment assignment or randomization

Interactive Response Technology (IRT) will be used for treatment assignment, patient allocation and drug supply management for all patients.

In addition, in Part 2, patients will be randomized to one of the 3 treatment arms ([Section 4.1](#) and [Section 6.1](#)) in a ratio of 1:1:1 through IRT.

The randomization numbers will be generated using the following procedure to ensure that treatment assignment is unbiased. A patient randomization list will be produced by the Interactive Response Technology (IRT) provider using a validated system that automates the random assignment of patient numbers to randomization numbers. These randomization numbers are linked to the different treatment arms, which in turn are linked to medication numbers. A separate medication randomization list will be produced by or under the responsibility of Novartis Drug Supply Management using a validated system that automates the random assignment of medication numbers to medication packs containing each of the study treatments.

Prior to dosing, all patients who fulfill all inclusion/exclusion criteria will be randomized via IRT to one of the treatment arms. The investigator or his/her delegate will call or log on to the IRT and confirm that the patient fulfills all the inclusion/exclusion criteria. The IRT will assign a randomization number to the patient, which will be used to link the patient to a treatment arm and will specify a unique medication number for the first package of study treatment to be dispensed to the patient. The randomization number will not be communicated to the caller.

For Japanese safety run-in part: Patients will be assigned by Novartis manually, outside IRT system. IRT will not be used for this part.

6.4.3 Treatment blinding

This is an open-label study.

6.5 Study drug preparation and dispensation

NIR178

The investigator or responsible site personnel must instruct the patient or caregiver to take the study drugs as per protocol. Study drug(s) will be dispensed to the patient by authorized site personnel only. All dosages prescribed to the patient and all dose changes during the study must be recorded on the Dosage Administration Record CRF.

PDR001

PDR001 (100 mg powder for solution for infusion) will be administered intravenously as a 30 minute infusion (up to 2 hours, if clinically indicated). Further instructions for the preparation and dispensation of PDR001 are described in the Pharmacy Manual.

6.5.1 Study treatment packaging and labeling

Study treatment, NIR178 and PDR001, will be provided as global clinical open-label patient specific supply and will be packed and labeled under the responsibility of Novartis, Drug Supply Management.

Medication labels will be in the local language and comply with the legal requirements of each country. They will include storage conditions for the drug but will not supply information about the patient.

NIR178 and PDR001 in different formulations and strengths can be used once they are approved.

Study treatment labels will comply with the legal requirements of each country and will include storage conditions, a unique medication number (corresponding to study treatment and strength). Site personnel will add the patient number on the label. If the label has 2-parts (base plus tear-off label), immediately before dispensing the package to the patient, site personnel will detach the outer part of the label from the package and affix it to the patient's source document.

For patients that are assigned by the IRT system, responsible site personnel will identify the study treatment package(s) to dispense by the medication number(s) assigned by IRT to the patient.

6.5.2 Drug supply and storage

Study treatments must be received by designated personnel at the study site, handled and stored safely and properly, and kept in a secured location to which only the investigator and designated site personnel have access. Upon receipt, the study treatment should be stored according to the instructions specified on the drug labels and in the [NIR178 (PBF-509) Investigator's Brochure] and [PDR001 Investigator's Brochure].

6.5.3 Study drug compliance and accountability

6.5.3.1 Study drug compliance

Compliance will be assessed by the investigator and/or study personnel at each patient visit and information provided by the patient and/or caregiver will be captured in the Drug Accountability Form. This information must be captured in the source document at each patient visit.

6.5.3.2 Study drug accountability

The investigator or designee must maintain an accurate record of the shipment and dispensing of study treatment in a drug accountability log. Drug accountability will be noted by the field monitor during site visits and at the completion of the study. Patients will be asked to return all unused study treatment and packaging on a regular basis, at the end of the study or at the time of study treatment discontinuation.

At study close-out, and, as appropriate during the course of the study, the investigator will return all used and unused study treatment, packaging, drug labels, and a copy of the completed drug accountability log to the Novartis monitor or to the Novartis address provided in the investigator folder at each site.

6.5.4 Disposal and destruction

The study drug supply can be destroyed at the local Novartis facility, Drug Supply group or third party, as appropriate. Drug supply can be destroyed at the site if permitted by local regulations.

7 Visit schedule and assessments

7.1 Study flow and visit schedule

Table 7-1, Table 7-2 and Table 7-3 lists all of the assessments and indicates with an “X”, the visits when they are performed. Japanese safety run-in part will be conducted in accordance with Table 7-1. Part 3 visit schedule will be followed by the continuous BID visit schedule (Table 7-1).

All data obtained from these assessments must be supported in the patient’s source documentation. The table (“Category” column) indicates which assessments produce data to be entered into the clinical database (D) or remain in source documents only (S).

No CRF will be used as a source document.

Screening evaluations must be performed ≤ 21 days of Cycle 1 Day 1 (except for the pregnancy test which must be performed within 72 hours before day 1 of every cycle and baseline imaging assessment which should be performed ≤ 28 days of Cycle 1 Day 1). Assessments performed as part of the screening evaluations and within 3 days prior to the first dose of study treatment, are not required to be repeated on Cycle 1 Day 1. Laboratory and radiological assessments performed as part of standard of care prior to signing informed consent may be used if performed within the screening time window.

During the course of the study visits, tests and/or procedures should occur on schedule whenever possible. A visit window of +/- 3 days is allowed for assessments except Imaging and PK.

Imaging assessments have an on study visit window of ± 1 week, regardless of dosing schedule or possible dose delays.

On PK collection days, the time windows are provided in Table 7-8 to Table 7-11. In situations when dosing is delayed, PK collections should also be delayed until the subsequent dose is given.

If the COVID-19 pandemic limits or prevents on-site study visits, alternative methods of providing continuing care may be implemented. Phone calls, virtual contacts (e.g. teleconsult) or visits by site staff/home nursing service to the patient’s home depending on local regulations and capabilities, can replace on-site study visits, for the duration of the pandemic until it is safe for the patient to visit the site again.

Table 7-1 Visit evaluation schedule for patients in Part 1, Part 2 NIR178 S1 (NIR178 Schedule 1-BID continuous dosing), Part 3 and Japanese safety run-in

Visit Name	Category	Protocol Section	Screening	Cycle 1 ^c					Cycle 2		Cycle 3		Day 1 of Subsequent cycles	End of study treatment (EoT)	Follow up *
				1	2	8	15	22	28	1	15	1			
Obtain Informed Consent	D	7.1.1.	X												
IRT Registration ^a	D	6.4, 7.1.1.1.	X												
Demography	D	7.1.1.3.	X												
Inclusion/exclusion criteria	D	5.2, 5.3.	X												
Medical History	D	7.1.1.3.	X												
Diagnosis and extent of cancer	D	7.1.1.3.	X												
Smoking History	D	7.1.1.3.	X												
Prior antineoplastic therapy	D	7.1.1.3.	X												
Prior/concomitant medications	D	7.1.1.3.	X	Throughout the study										X	X
Baseline tumor molecular characteristics	D	7.1.1.3.	X												
Antineoplastic therapies since discontinuation of study treatment	D	7.1.5, 7.1.6, 7.1.7.												X	X
IRT Randomization ^a		6.4.	X											X	
Physical examination	S	7.2.2.1.	X	X			X			X	X (for Japanese safety run-in only)	X		X	X
Performance status	D	7.2.2.4.	X	X						X		X		X	X
Height	D	7.2.2.3.	X												
Weight	D	7.2.2.3.	X	X						X		X		X	X

Visit Name	Category	Protocol Section	Screening	Cycle 1 ^c					Cycle 2		Cycle 3		Day 1 of Subsequent cycles	End of study treatment (EoT)	Follow up *	
				1	2	8	15	22	28	1	15	1				15
Day of cycle				1	2	8	15	22	28	1	15	1	15			
Vital signs	D	7.2.2.2.	X	X			X			X	X	X	X	X	X	
Hematology	D	7.2.2.5.1.	X	X			X			X	X	X	X	X	X	
Chemistry	D	7.2.2.5.2.	X	X			X			X	X	X	X	X	X	
Thyroid Panel (TSH, free T4, T3)	D	7.2.2.5.4.	X				X			X	X	X	X	X	X	
Coagulation (PTT/aPTT and PT or INR)	D	7.2.2.5.3.	X	If Clinically indicated												
Creatinine clearance	D	7.2.2.5.2.	X	X												
Hepatitis testing	D	7.2.2.5.5.	X													
HIV testing	D	7.2.2.5.5.	X													
Urinalysis (microscopic or macroscopic)	D	7.2.2.5.8.	X	If Clinically indicated												
Pregnancy test	D	7.2.2.5.7.	X	X						X		X		X	X	X
PSA (only for mCRPC patients)	D	7.2.2.5.8	X	X						X		X		X	X	
Disease assessment/Tumor evaluation per iRECIST, RECIST v 1.1 or Cheson et al (2014) for lymphoma, color photography of visible lesion(s) and PCWG3	D	7.2.1.	X									Every 8 weeks from C1D1 for 40 weeks and every 12 weeks thereafter until progression of disease per iRECIST or Cheson et al (2014) or patient withdrawal		X (If not performed within 30 days prior to EOT)		
Bone marrow biopsy or aspirate in patients with known bone marrow involvement (for Lymphoma only)	D	7.2.1.	X													
12 lead ECG	D	7.2.2.7.	X	X					X	X		X		X	X	
Adverse events	D	8.	X	Throughout the study										X	X	

Visit Name	Category	Protocol Section	Screening	Cycle 1 ^c						Cycle 2		Cycle 3		Day 1 of Subsequent cycles	End of study treatment (EoT)	Follow up *	
				1	2	8	15	22	28	1	15	1	15				
NIR178 dosing	D	6.1.		As per assigned schedule													
PDR001 infusion	D	6.1.		X ^a						X		X		X			
PK sampling for NIR178, NJI765 and PDR001 ^b	D	7.2.3.		X	X	X	X	X	X	X		X	X	X (up to cycle 6)	X		
Chest X-ray (For Japan only)	D	7.2.2.6.	X				X				X						

*Please refer to Section 7.1.5 for safety follow up, Section 7.1.6 for disease progression follow up, Section 7.1.7 for survival follow up and Section 7.1.8 for information on lost to follow-up patients. a: Not applicable for Japanese safety run-in; An optional tumor sample may also be collected at disease progression when patients continue on study treatment due to overall clinical benefit b: Please refer to Section 7.2.3. for Japanese safety run-in; c: Patients will be hospitalized during first cycle for Japanese safety run-in.
																	

[figure not shown]
[figure not shown]
[figure not shown]

Table 7-2 Visit evaluation schedule for patients in Part 2 NIR178 S 2 (NIR178 Schedule 2 regimen-two weeks on two weeks off dosing)

Visit Name	Category	Protocol Section	Screening	Cycle 1					Cycle 2		Cycle 3		Day 1 of Subsequent cycles	End of study treatment (EoT)	Follow up *	
				1	2	8	14	15	22	1	15	1				15
Obtain Informed Consent	D	7.1.1.	X													
IRT Registration	D	6.4, 7.1.1.1.	X													
Demography	D	7.1.1.3.	X													
Inclusion/exclusion criteria	D	5.2, 5.3.	X													
Medical History	D	7.1.1.3.	X													
Smoking history	D	7.1.1.3.	X													
Diagnosis and extent of cancer	D	7.1.1.3.	X													
Prior antineoplastic therapy	D	7.1.1.3.	X													
Prior/concomitant medications	D	7.1.1.3.	X	Throughout the study										X	X	
Antineoplastic therapies since discontinuation of study treatment	D	7.1.5, 7.1.6, 7.1.7.													X	X
IRT Randomization		6.4.	X												X	
Physical examination	S	7.2.2.1.	X	X				X		X		X		X	X	
Performance status	D	7.2.2.4.	X	X						X		X		X	X	
Height	D	7.2.2.3.	X													
Weight	D	7.2.2.3.	X	X						X		X		X	X	
Vital signs	D	7.2.2.2.	X	X				X		X	X	X	X	X	X	
Hematology	D	7.2.2.5.1.	X	X				X		X	X	X	X	X	X	
Chemistry	D	7.2.2.5.2.	X	X				X		X	X	X	X	X	X	
Thyroid Panel (TSH, free T4, T3)	D	7.2.2.5.4.	X					X		X	X	X	X	X	X	
Coagulation (PTT/aPTT and PT or INR)	D	7.2.2.5.3.	X	If Clinically indicated												

Visit Name	Category	Protocol Section	Screening	Cycle 1						Cycle 2		Cycle 3		Day 1 of Subsequent cycles	End of study treatment (EoT)	Follow up *		
				1	2	8	14	15	22	1	15	1	15					
Day of cycle				1	2	8	14	15	22	1	15	1	15					
Creatinine clearance	D	7.2.2.5.2.	X	X														
Hepatitis testing	D	7.2.2.5.5.	X															
HIV testing	D	7.2.2.5.5.	X															
Urinalysis (microscopic or macroscopic)	D	7.2.2.5.8.	X	If Clinically indicated														
Pregnancy test	D	7.2.2.5.7.	X	X						X		X		X	X	X		
Disease assessment/Tumor evaluation per iRECIST, RECIST v 1.1 or Cheson et al (2014) for lymphoma, color photography of visible lesion(s)	D	7.2.1.	X									Every 8 weeks from C1D1 for 40 weeks and every 12 weeks thereafter until progression of disease per iRECIST or Cheson et al (2014) or patient withdrawal			X (If not performed within 30 days prior to EOT)			
12 lead ECG	D	7.2.2.7.	X	X			X			X		X		X	X			
Adverse events	D	8.	X	Throughout the study											X	X		
NIR178 dosing	D	6.1.		As per assigned schedule														
PDR001 infusion	D	6.1.		X						X		X		X				

Visit Name	Category	Protocol Section	Screening	Cycle 1						Cycle 2		Cycle 3		Day 1 of Subsequent cycles	End of study treatment (EoT)	Follow up *
				1	2	8	14	15	22	1	15	1	15			
PK sampling for NIR178, NJI765 and PDR001	D	7.2.3.		X	X	X	X	X	X	X		X	X	X (up to cycle 6)	X	

*Please refer to Section 7.1.5 for safety follow up, Section 7.1.6 for disease progression follow up, Section 7.1.7 for survival follow up and Section 7.1.8 for information on lost to follow-up patients.
 
a: An optional tumor sample may be collected at disease progression when patients continue on study treatment due to overall clinical benefit.
																

[figure not shown]
[figure not shown]
[figure not shown]

Table 7-3 Visit evaluation schedule for patients in Part 2 NIR178 S3 (NIR178 Schedule 3-one week on, one week of dosing)

[figure not shown]
Visit Name	Category	Protocol Section	Screening	Cycle 1						Cycle 2		Cycle 3		Day 1 of Subsequent cycles	End of study treatment (EoT)	Follow up *	
				1	2	7	8	15	22	1	15	1	15				
Obtain Informed Consent	D	7.1.1.	X														
IRT Registration	D	6.4, 7.1.1.1.	X														
Demography	D	7.1.1.3.	X														
Inclusion/exclusion criteria	D	5.2, 5.3.	X														
Medical History	D	7.1.1.3.	X														
Smoking history	D	7.1.1.3.															
Diagnosis and extent of cancer	D	7.1.1.3.	X														
Prior antineoplastic therapy	D	7.1.1.3.	X														
Prior/concomitant medications	D	7.1.1.3.	X	Throughout the study										X	X		
Antineoplastic therapies since discontinuation of study treatment	D	7.1.5, 7.1.6, 7.1.7.													X	X	
IRT Randomization		6.4.	X												X		
Physical examination	S	7.2.2.1.	X	X				X		X		X		X	X		
Performance status	D	7.2.2.4.	X	X						X		X		X	X		
Height	D	7.2.2.3.	X														
Weight	D	7.2.2.3.	X	X						X		X		X	X		
Vital signs	D	7.2.2.2.	X	X				X		X	X	X	X	X	X		
Hematology	D	7.2.2.5.1.	X	X				X		X	X	X	X	X	X		
Chemistry	D	7.2.2.5.2.	X	X				X		X	X	X	X	X	X		
Thyroid Panel (TSH, free T4, T3)	D	7.2.2.5.4.	X					X		X	X	X	X	X	X		
Coagulation (PTT/aPTT and PT or INR)	D	7.2.2.5.3.	X	If Clinically indicated													
Creatinine clearance	D	7.2.2.5.2.	X	X													

Visit Name	Category	Protocol Section	Screening	Cycle 1						Cycle 2		Cycle 3		Day 1 of Subsequent cycles	End of study treatment (EoT)	Follow up *		
				1	2	7	8	15	22	1	15	1	15					
Day of cycle				1	2	7	8	15	22	1	15	1	15					
Hepatitis testing	D	7.2.2.5.5.	X															
HIV testing	D	7.2.2.5.5.	X															
Urinalysis (microscopic or macroscopic)	D	7.2.2.5.8.	X	If Clinically indicated														
Pregnancy test	D	7.2.2.5.7.	X	X						X		X		X	X	X		
Disease assessment/Tumor evaluation per iRECIST, RECIST v 1.1 or Cheson et al (2014) for lymphoma, color photography of visible lesion(s)	D	7.2.1.	X									Every 8 weeks from C1D1 for 40 weeks and every 12 weeks thereafter until progression of disease per iRECIST or Cheson et al (2014) or patient withdrawal		X (If not performed within 30 days prior to EOT)				
12 lead ECG	D	7.2.2.7.	X	X		X				X		X		X	X			
Adverse events	D	8.	X	Throughout the study										X	X			
NIR178 dosing	D	6.1.		As per assigned schedule														
PDR001 infusion	D	6.1.		X						X		X		X				

Visit Name	Category	Protocol Section	Screening	Cycle 1						Cycle 2		Cycle 3		Day 1 of Subsequent cycles	End of study treatment (EoT)	Follow up *
				1	2	7	8	15	22	1	15	1	15			
Day of cycle				1	2	7	8	15	22	1	15	1	15			
PK sampling for NIR178, NJI765 and PDR001	D	7.2.3.		X	X	X	X	X	X	X		X	X	X (up to cycle 6)	X	

*Please refer to Section 7.1.5 for safety follow up, Section 7.1.6 for disease progression follow up, Section 7.1.7 for survival follow up and Section 7.1.8 for information on lost to follow-up patients.
 
a: An optional tumor sample may be collected at disease progression when patients continue on study treatment due to overall clinical benefit.
																

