Additionally, as per recommendation of the Japanese Health Authority, a safety run-in part will be conducted in Japanese patients dosed at either 80mg or 160mg BID of NIR178 for the first cycle of treatment. The data generated from the safety run-in is considered adequate to evaluate the safety and pharmacokinetic (PK) profiles of single agent NIR178. Since there were no differences in the safety and PK profiles of PDR001 between Japanese and non-Japanese patients treated at the RDE of 400mg IV Q4 weeks in study CPDR001X1101, and given the low likelihood of DDI between NIR178 and PDR001 ([Section 2.4.1](#)), following the first cycle safety run-in patients who receive single-agent NIR178 will be treated with the combination of NIR178+PDR001 starting cycle 2 onwards ([Section 4.1.4](#)). While the final analysis of safety will use all available safety and pharmacokinetic data (including combination phase with PDR001), the safety of single agent NIR178 in Japanese patients in relation to that of non-Japanese patients treated at the same dose levels in the phase I study CNIR178X2103J, will be the primary determinant of whether or not Japanese patients can join the phase II study. As of Protocol Amendment 6, patients enrolled in the Japanese safety run-in part of the study will be treated with NIR178 240mg hard gelatin capsules BID in combination with PDR001 400mg Q4W starting at Cycle 1 Day 1. Based on the data from the Japanese safety run-in at the 80mg and 160mg, there were no obvious ethnic differences on safety and PK observed between Japanese versus non-Japanese patients. In addition, no DDI has been observed between NIR178 and PDR001. This design also allows Novartis to assess DLT in combination therapy in Japanese patients at the recommended dose.

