
4.1.4 Japanese safety run-in part

A separate safety run-in part will be conducted in Japan in order to adequately characterize the safety and pharmacokinetic profiles of NIR178 as a single-agent (Figure 4-2). Patients enrolled in this part will be excluded from the primary analysis for efficacy and will also be exempt from the mandatory paired biopsy requirement.

Patients enrolled in the safety run-in part must be hospitalized for the first cycle of therapy for safety monitoring. Patients will receive NIR178 as single agent for the first cycle (28 days). If the patients complete cycle 1 without experiencing DLTs (see Table 6-3), they will initiate combination therapy with PDR001 400mg IV q4weeks starting cycle 2 onwards, and continue at the same dose of NIR178. Patients who experience a DLT in cycle 1 will be permanently discontinued from the study treatment and will not proceed to combination therapy. Patients will continue on combination therapy until they experience unacceptable toxicity, confirmed disease progression per iRECIST or Cheson et al (2014) for DLBCL and/or treatment is discontinued at the discretion of the investigator or the patient.

As of Amendment 6, newly enrolled patients in the Japanese safety run-in will receive NIR178 240mg BID in combination with PDR001 400mg IV Q4W starting Cycle 1 day 1. If the patients complete cycle 1 without experiencing DLTs, they will continue on the same combination therapy of NIR178 and PDR001.

In the CPDR001X1101 study of single agent PDR001 in Japanese patients, the safety and PK of PDR001 for Japanese patients were similar between Japanese and non-Japanese patients and the recommended dose determined for PDR001 in non-Japanese patients was found to be acceptable for Japanese patients. Therefore, the dose for PDR001 in the safety run-in part will be 400 mg IV Q4 weeks.

The period for evaluating DLTs will be cycle 1 (i.e. the first 28 days of treatment with single agent NIR178). **Patients must complete a minimum of 80% of planned therapy during cycle 1 with the minimum safety evaluation and drug exposure or have had a DLT within the first cycle of treatment to be considered evaluable for dose escalation decisions. Dose escalation decisions will occur when the cohort of patients has met these criteria.** Upon comprehensive review of all available safety, PK, and PD data (including that of the

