In the Japanese safety run-in part, patients will take NIR178 at 80 or 160mg twice daily continuously during the Cycle 1, and then starting from Cycle 2D1, will receive NIR178 twice daily continuously in combination with PDR001 400mg administered once on day 1 every 28 days. The starting dose of NIR178 80mg is 50% of the RoW starting dose at which no DLT was observed in the CNIR178X2103J phase I/Ib study in combination with PDR001. As of protocol amendment 6, patients enrolled in the Japanese safety run-in part will receive NIR178 240mg twice daily in combination with PDR001 400 mg administered on day 1 of every 28 day cycles.

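### Table 7-1 and the Section 4.1.4 DLT window were not updated for Amendment 6, so the protocol states two different Cycle 1 treatments for the Japanese 240 mg run-in

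*Protocol*

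**What the plan says.** Section 7.1 makes one schedule govern the run-in: "Japanese safety run-in part will be conducted in accordance with Table 7-1". In the row headed "PDR001 infusion", the Cycle 1 Day 1 cell is marked a; the cells for Cycle 2, Cycle 3 and later cycles are not. Footnote a begins "a: Not applicable for Japanese safety run-in".

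Section 4.1.4 says that newly enrolled run-in patients under Amendment 6 "will receive NIR178 240mg BID in combination with PDR001 400mg IV Q4W starting Cycle 1 day 1". Section 6.1.1 says that they "will receive NIR178 240mg twice daily in combination with PDR001 400 mg administered on day 1 of every 28 day cycles". Section 2.2 gives the purpose: "This design also allows Novartis to assess DLT in combination therapy in Japanese patients at the recommended dose".

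On the DLT window, Section 4.1.4 reads "The period for evaluating DLTs will be cycle 1 (i.e. the first 28 days of treatment with single agent NIR178". Section 10.8 and the run-in text at the end of SAP Section 3.3 use the same definition but extend it to treatment in combination with PDR001. SAP Section 1.1.4 defines the window simply as the first cycle.

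The 240 mg rule in Section 4.1.4 allows the combination to be declared safe in Japanese patients on 0/3, or no more than 1/6, Cycle 1 DLTs, after review of all available safety, PK and PD data.

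**The concern.** DLTs are counted only in Cycle 1. What is given in Cycle 1 therefore determines what the DLT count measures. Read literally, the schedule that governs the run-in removes PDR001 from that cycle, and the DLT-window sentence in Section 4.1.4 agrees with it. The regimen text puts PDR001 on Day 1 of the same cycle.

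A site cannot comply with both, and Section 12 permits no authorised deviations. At stake is whether the count behind a decision about the 240 mg combination comes from patients who received the combination during the window.

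**Working it through.** The documents state no sample size justification, power or error rate for the run-in, so there is no figure to reproduce. The check is a cross-reading.

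**1. Is the marker a real exclusion?** Footnote a has two clauses: the run-in exclusion, and a note on an optional tumour sample, which has no meaning on an infusion row. In Tables 7-2 and 7-3 footnote a has only the tumour-sample clause, and there the Cycle 1 Day 1 PDR001 cell is unmarked. So in Table 7-1 the marker carries the run-in exclusion.

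**2. Where does it come from?** It fits the 80 mg and 160 mg design described in Sections 4.1.4 and 6.1.1: NIR178 alone in Cycle 1, PDR001 from Cycle 2. The same footnote sits on the two IRT rows, where it agrees with Section 6.4, which keeps the run-in outside IRT.

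**3. PDR001 infusions in the 28-day DLT window, 240 mg cohort.**
- Table 7-1 as written: 0.
- Sections 2.2, 2.3, 4.1.4 (Amendment 6 text) and 6.1.1: 1, on Day 1.
- Table 7-8 footnote e: PDR001 sampling starts in Cycle 1 for patients enrolled under Amendment 6, which presupposes the infusion.
- SAP Section 1.1.4: combination from Cycle 1.

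**4. Other signs of an incomplete update.** Table 7-8 separates the enrolment eras and Table 7-1 does not. Section 4.1.4 announces two dose levels; Section 10.8 says three.

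**5. Can the effect on the rule be sized?** Let p be the true Cycle 1 DLT rate. The documented rule clears the dose with probability

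P(clear) = (1−p)³ + 3p(1−p)² × (1−p)³, and P(terminate) = 1 − P(clear).

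Section 1.2.1.4 reports 4 DLTs among 25 combination patients, with dose levels pooled. It reports 2 among 25 single-agent patients, both at 640 mg, so 0 among the 3+3+7+6 = 19 at 480 mg or below. Using these as stand-ins for p is an assumption.
- p = 4/25 = 0.16: 0.84³ = 0.593 and 3×0.16×0.84² = 0.339. P(clear) = 0.593 + 0.339×0.593 = 0.793 (from unrounded terms). P(terminate) = 0.207.
- Exact 95% interval for 4/25, 4.5% to 36%:
  - p = 0.045: P(clear) = 0.871 + 0.123×0.871 = 0.978, so P(terminate) is about 2%.
  - p = 0.36: P(clear) = 0.262 + 0.442×0.262 = 0.378, so P(terminate) is about 62%.
- Exact 95% upper limit for 0/19, 17.6%: P(clear) = 0.559 + 0.359×0.559 = 0.760, so P(terminate) is about 24%.

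The two ranges overlap, so these data do not establish how far the rule would behave differently with and without PDR001 in the window.

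**The case against.** The strongest defence is that this is one stale footnote and one stale parenthesis against consistent regimen text in five protocol sections, Table 7-8 and the SAP. Section 7.1 introduces Table 7-1 as a list of assessments, and its PDR001 row refers back to Section 6.1.

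Several provisions would also expose a missed infusion:
- The 240 mg rule is worded for patients treated in combination with PDR001.
- Table 7-8 asks for a PDR001 sample one hour after the Cycle 1 infusion.
- Patients are in hospital for Cycle 1.
- The safety declaration requires review of all data.

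Much of this stands. A reader might infer that the protocol would in practice clear the 240 mg combination on single-agent data, or that the decision would say nothing about the combination. The documents do not support either reading. The rule's own wording excludes a cohort given NIR178 alone, and even under Table 7-1 PDR001 starts in Cycle 2 and those data are part of the review. Nothing shows that any patient was dosed from the table.

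The contradiction itself remains. No passage ranks the body text above Table 7-1, and Section 7.1 names that table for conduct of the run-in. The requirement to complete 80% of planned Cycle 1 therapy does not settle the matter, because what is planned is the point in dispute. Data review can detect an omitted infusion, but cannot turn a single-agent DLT count into a combination count.

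**Conclusion.** The concern holds as an internal contradiction left by an incomplete amendment. Table 7-1 (PDR001 row, footnote a) and the DLT-window sentence in Section 4.1.4 disagree with the rest of the protocol and with the SAP on Cycle 1 for patients enrolled under Amendment 6. If Table 7-1 were followed, the DLT window would contain 0 PDR001 infusions instead of 1. That consequence is conditional and detectable.

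A reader might also contrast 21% termination at the pooled combination rate with almost none on single-agent data. The documents do not support this. They give no DLT rate at 240 mg, 4/25 pools dose levels, and 0/19 does not mean a true rate of zero. Any operating figure is an assumption over a wide range, about 2% to 62% across the interval for 4/25, and the finding does not depend on it.

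No view is taken on which Cycle 1 treatment is right. SAP Section 4 says that the study is closed out, so the remaining practical value lies mainly in reporting.

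**What to change.** Reconcile the PDR001 row of Table 7-1 and its footnote, and the DLT-window sentence in Section 4.1.4, with Sections 2.2, 2.3, 6.1.1 and 10.8, Table 7-8 and the SAP. Cycle 1 treatment and the DLT window should be stated once for each enrolment era, as Table 7-8 does with footnote e. Footnote a can stay on the IRT rows.

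In the SAP or study report, present Cycle 1 DLTs for any 240 mg run-in patient beside that patient's actual Cycle 1 exposure to NIR178 and to PDR001. SAP Section 2.6.2.6.3 plans DLT summaries for the run-in but does not ask for this pairing.

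No new evaluability rule is needed. Requiring both drugs before a patient counts would conflict with Section 4.1.4, where a Cycle 1 DLT alone makes a patient evaluable.

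The cost is one footnote, one sentence and one reporting line, with no extra patients or visits.
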